7.2.3 Immediate Reporting of Adverse Events to the Sponsor

7.2.3.1 Serious Adverse Events

A serious adverse event is any adverse event occurring at any dose or during any use of Sponsor's product that:

- Results in death;
- Is life threatening;
- Results in persistent or significant disability/incapacity;
- Results in or prolongs an existing inpatient hospitalization;
- Is a congenital anomaly/birth defect;
- Is an other important medical event

Note: In addition to the above criteria, adverse events meeting either of the below criteria, although not serious per ICH definition, are reportable to the Sponsor in the same timeframe as SAEs to meet certain local requirements. Therefore, these events are considered serious by the Sponsor for collection purposes.

- Is a cancer;
- Is associated with an overdose.

Refer to [Table 10](#) for additional details regarding each of the above criteria.

For the time period beginning when the consent form is signed until randomization/treatment allocation, any serious adverse event, or follow up to a serious adverse event, including death due to any cause other than progression of the cancer under study (reference Section 7.2.3.3 for additional details), that occurs to any subject must be reported within 24 hours to the Sponsor if it causes the subject to be excluded from the trial, or is the result of a protocol-specified intervention, including but not limited to washout or discontinuation of usual therapy, diet, placebo treatment or a procedure.

For the time period beginning at randomization/treatment allocation through 90 days following cessation of treatment, or 30 days following cessation of treatment if the subject initiates new anticancer therapy, whichever is earlier, any serious adverse event, or follow up to a serious adverse event, including death due to any cause other than progression of the

cancer under study (reference Section 7.2.3.3 for additional details), whether or not related to the Sponsor's product, must be reported within 24 hours to the Sponsor either by electronic media or paper. Electronic reporting procedures can be found in the EDC data entry guidelines. Paper reporting procedures can be found in the Investigator Trial File Binder (or equivalent).

Additionally, any serious adverse event, considered by an investigator who is a qualified physician to be related to the Sponsor's product that is brought to the attention of the investigator at any time outside of the time period specified in the previous paragraph also must be reported immediately to the Sponsor.

All subjects with serious adverse events must be followed up for outcome.

7.2.3.2 Events of Clinical Interest

Selected non-serious and serious adverse events are also known as Events of Clinical Interest (ECI) and must be reported to the Sponsor.

For the time period beginning when the consent form is signed until randomization/treatment allocation, any ECI, or follow up to an ECI, that occurs to any subject must be reported within 24 hours to the Sponsor if it causes the subject to be excluded from the trial, or is the result of a protocol-specified intervention, including but not limited to washout or discontinuation of usual therapy, diet, placebo treatment or a procedure.

For the time period beginning at randomization/treatment allocation through 90 days following cessation of treatment, or 30 days following cessation of treatment if the subject initiates new anticancer therapy, whichever is earlier, any ECI, or follow up to an ECI, whether or not related to the Sponsor's product, must be reported within 24 hours to the Sponsor, either by electronic media or paper. Electronic reporting procedures can be found in the EDC data entry guidelines. Paper reporting procedures can be found in the Investigator Trial File Binder (or equivalent).

Events of clinical interest for this trial include:

- an overdose of Sponsor's product, as defined in Section 7.2.1 - Definition of an Overdose for This Protocol and Reporting of Overdose to the Sponsor, that is not associated with clinical symptoms or abnormal laboratory results.
- an elevated AST or ALT lab value that is greater than or equal to 3X the upper limit of normal and an elevated total bilirubin lab value that is greater than or equal to 2X the upper limit of normal and, at the same time, an alkaline phosphatase lab value that is less than 2X the upper limit of normal, as determined by way of protocol-specified laboratory testing or unscheduled laboratory testing.*

***Note:** These criteria are based upon available regulatory guidance documents. The purpose of the criteria is to specify a threshold of abnormal hepatic tests that may require an additional evaluation for an underlying etiology. The trial site guidance for

assessment and follow up of these criteria can be found in the Investigator Trial File Binder (or equivalent).

- Post-transplant complications (see Sec 7.1.5.4.1) that occurred within 18 months from the date of the allogeneic transplant, for subjects who were previously exposed to pembrolizumab.
- Additional Adverse Events:

Events of Clinical Interest identified from the date of first dose through 90 days following cessation of treatment, or 30 days after the initiation of a new anticancer therapy, whichever is earlier need to be reported to the Sponsor within 24 hours of the event consistent with standard SAE reporting guidelines and either by electronic media or paper. Sponsor Contact information can be found in the administrative binder.

Subjects should be assessed for possible ECIs prior to each dose. Lab results should be evaluated and subjects should be asked for signs and symptoms suggestive of an immune-related event. Subjects who develop an ECI thought to be immune-related should have additional testing to rule out other etiologic causes. If lab results or symptoms indicate a possible immune-related ECI, then additional testing should be performed to rule out other etiologic causes. If no other cause is found, then it is assumed to be immune-related.

7.2.3.3 Protocol-Specific Exceptions to Serious Adverse Event Reporting

Efficacy endpoints as outlined in this section will not be reported to the Sponsor as described in Section 7.2.3. Immediate Reporting of Adverse Events to the Sponsor.

Specifically, the suspected/actual events covered in this exception include any event that is disease progression of the cancer under study.

The Sponsor will monitor unblinded aggregated efficacy endpoint events and safety data to ensure the safety of the subjects in the trial. Any suspected endpoint which upon review is not progression of the cancer under study will be forwarded to global safety as a SAE within 24 hours of determination that the event is not progression of the cancer under study.

7.2.4 Evaluating Adverse Events

An investigator who is a qualified physician will evaluate all adverse events according to the NCI Common Terminology for Adverse Events (CTCAE), version 4.0. Any adverse event which changes CTCAE grade over the course of a given episode will have each change of grade recorded on the adverse event case report forms/worksheets.

All adverse events regardless of CTCAE grade must also be evaluated for seriousness.

Table 10 Evaluating Adverse Events

An investigator who is a qualified physician, will evaluate all adverse events as to:

V4.0 CTCAE Grading	Grade 1	Mild; asymptomatic or mild symptoms; clinical or diagnostic observations only; intervention not indicated.
	Grade 2	Moderate; minimal, local or noninvasive intervention indicated; limiting age-appropriate instrumental ADL.
	Grade 3	Severe or medically significant but not immediately life-threatening; hospitalization or prolongation of hospitalization indicated; disabling; limiting self-care ADL.
	Grade 4	Life threatening consequences; urgent intervention indicated.
	Grade 5	Death related to AE
Seriousness	A serious adverse event is any adverse event occurring at any dose or during any use of Sponsor's product that:	
	† Results in death; or	
	† Is life threatening; or places the subject, in the view of the investigator, at immediate risk of death from the event as it occurred (Note: This does not include an adverse event that, had it occurred in a more severe form, might have caused death.); or	
	† Results in a persistent or significant disability/incapacity (substantial disruption of one's ability to conduct normal life functions); or	
	† Results in or prolongs an existing inpatient hospitalization (hospitalization is defined as an inpatient admission, regardless of length of stay, even if the hospitalization is a precautionary measure for continued observation. (Note: Hospitalization for an elective procedure to treat a pre-existing condition that has not worsened is not a serious adverse event. A pre-existing condition is a clinical condition that is diagnosed prior to the use of an MSD product and is documented in the patient's medical history.); or	
	† Is a congenital anomaly/birth defect (in offspring of subject taking the product regardless of time to diagnosis); or	
	Is a cancer (although not serious per ICH definition, is reportable to the Sponsor within 24 hours to meet certain local requirements); or	
	Is associated with an overdose (whether accidental or intentional). Any adverse event associated with an overdose is considered a serious adverse event for collection purposes. An overdose that is not associated with an adverse event is considered a non-serious event of clinical interest and must be reported within 24 hours.	
	Other important medical events that may not result in death, not be life threatening, or not require hospitalization may be considered a serious adverse event when, based upon appropriate medical judgment, the event may jeopardize the subject and may require medical or surgical intervention to prevent one of the outcomes listed previously (designated above by a †).	
	Duration Record the start and stop dates of the adverse event. If less than 1 day, indicate the appropriate length of time and units	
Action taken	Did the adverse event cause the Sponsor's product to be discontinued?	
Relationship to Sponsor's Product	Did the Sponsor's product cause the adverse event? The determination of the likelihood that the Sponsor's product caused the adverse event will be provided by an investigator who is a qualified physician. The investigator's signed/dated initials on the source document or worksheet that supports the causality noted on the AE form, ensures that a medically qualified assessment of causality was done. This initialed document must be retained for the required regulatory time frame. The criteria below are intended as reference guidelines to assist the investigator in assessing the likelihood of a relationship between the test drug and the adverse event based upon the available information.	
	The following components are to be used to assess the relationship between the Sponsor's product and the AE; the greater the correlation with the components and their respective elements (in number and/or intensity), the more likely the Sponsor's product caused the adverse event (AE):	
	Exposure	Is there evidence that the subject was actually exposed to the Sponsor's product such as: reliable history, acceptable compliance assessment (pill count, diary, etc.), expected pharmacologic effect, or measurement of drug/metabolite in bodily specimen?
	Time Course	Did the AE follow in a reasonable temporal sequence from administration of the Sponsor's product? Is the time of onset of the AE compatible with a drug-induced effect (applies to trials with investigational medicinal product)?
	Likely Cause	Is the AE not reasonably explained by another etiology such as underlying disease, other drug(s)/vaccine(s), or other host or environmental factors

Relationship	The following components are to be used to assess the relationship between the test drug and the AE: (continued)							
to Sponsor's Product (continued)	Dechallenge	
Was the Sponsor's product discontinued or dose/exposure/frequency reduced? If yes, did the AE resolve or improve? If yes, this is a positive dechallenge. If no, this is a negative dechallenge.
 
(Note: This criterion is not applicable if: (1) the AE resulted in death or permanent disability; (2) the AE resolved/improved despite continuation of the Sponsor's product; or (3) the trial is a single-dose drug trial); or (4) Sponsor's product(s) is/are only used one time.)
						
	Rechallenge	
Was the subject re-exposed to the Sponsor's product in this study? If yes, did the AE recur or worsen? If yes, this is a positive rechallenge. If no, this is a negative rechallenge.
 
(Note: This criterion is not applicable if: (1) the initial AE resulted in death or permanent disability, or (2) the trial is a single-dose drug trial); or (3) Sponsor's product(s) is/are used only one time).
 
NOTE: IF A RECHALLENGE IS PLANNED FOR AN ADVERSE EVENT WHICH WAS SERIOUS AND WHICH MAY HAVE BEEN CAUSED BY THE SPONSOR'S PRODUCT, OR IF REEXPOSURE TO THE SPONSOR'S PRODUCT POSES ADDITIONAL POTENTIAL SIGNIFICANT RISK TO THE SUBJECT, THEN THE RECHALLENGE MUST BE APPROVED IN ADVANCE BY THE SPONSOR CLINICAL DIRECTOR AS PER DOSE MODIFICATION GUIDELINES IN THE PROTOCOL.
						
	Consistency with Trial Treatment Profile	Is the clinical/pathological presentation of the AE consistent with previous knowledge regarding the Sponsor's product or drug class pharmacology or toxicology?						

The assessment of relationship will be reported on the case report forms /worksheets by an investigator who is a qualified physician according to his/her best clinical judgment, including consideration of the above elements.
								

Record one of the following
 
  
 Record one of the following	Use the following scale of criteria as guidance (not all criteria must be present to be indicative of a Sponsor's product relationship).	
   
 Yes, there is a reasonable possibility of Sponsor's product relationship.	There is evidence of exposure to the Sponsor's product. The temporal sequence of the AE onset relative to the administration of the Sponsor's product is reasonable. The AE is more likely explained by the Sponsor's product than by another cause.	
 
 No, there is not a reasonable possibility of Sponsor's product relationship	Subject did not receive the Sponsor's product OR temporal sequence of the AE onset relative to administration of the Sponsor's product is not reasonable OR the AE is more likely explained by another cause than the Sponsor's product. (Also entered for a subject with overdose without an associated AE.)	
  
			Record one of the following	Use the following scale of criteria as guidance (not all criteria must be present to be indicative of a Sponsor's product relationship).	Yes, there is a reasonable possibility of Sponsor's product relationship.	There is evidence of exposure to the Sponsor's product. The temporal sequence of the AE onset relative to the administration of the Sponsor's product is reasonable. The AE is more likely explained by the Sponsor's product than by another cause.	No, there is not a reasonable possibility of Sponsor's product relationship	Subject did not receive the Sponsor's product OR temporal sequence of the AE onset relative to administration of the Sponsor's product is not reasonable OR the AE is more likely explained by another cause than the Sponsor's product. (Also entered for a subject with overdose without an associated AE.)
Record one of the following	Use the following scale of criteria as guidance (not all criteria must be present to be indicative of a Sponsor's product relationship).							
Yes, there is a reasonable possibility of Sponsor's product relationship.	There is evidence of exposure to the Sponsor's product. The temporal sequence of the AE onset relative to the administration of the Sponsor's product is reasonable. The AE is more likely explained by the Sponsor's product than by another cause.							
No, there is not a reasonable possibility of Sponsor's product relationship	Subject did not receive the Sponsor's product OR temporal sequence of the AE onset relative to administration of the Sponsor's product is not reasonable OR the AE is more likely explained by another cause than the Sponsor's product. (Also entered for a subject with overdose without an associated AE.)							

7.2.5 Sponsor Responsibility for Reporting Adverse Events

All Adverse Events will be reported to regulatory authorities, IRB/IECs and investigators in accordance with all applicable global laws and regulations, i.e., per ICH Topic E6 (R1) Guidelines for Good Clinical Practice.

8.0 STATISTICAL ANALYSIS PLAN

This section outlines the statistical analysis strategy and procedures for the study. If changes are made to the primary and/or key secondary hypotheses, or the statistical methods related to those hypotheses post study initiation and prior to final database lock, the protocol will be amended (consistent with ICH Guideline E-9). After the protocol has been finalized and prior to the final database lock any changes to exploratory or other non-confirmatory analyses, will be documented in a supplemental SAP (sSAP) and referenced in the Clinical Study Report (CSR) for the study. Post hoc exploratory analyses will also be identified in the CSR.

Unless specified otherwise, the statistical analyses will be conducted separately by cohort. In addition, a separate CSR may be issued for a single cohort if the actual enrollment rate among cohorts is markedly different.

8.1 Statistical Analysis Plan Summary

Key elements of the statistical analysis plan are summarized in [Table 11](#) below; the comprehensive plan is provided in Sections 8.2-8.12.

Table 11 Statistical Analysis Plan Summary

Study Design Overview	This study, “A Phase II clinical trial of MK-3475 (pembrolizumab) in subjects with relapsed or refractory (R/R) classical Hodgkin Lymphoma (cHL)” is a multicenter, single arm, multi-cohort, nonrandomized trial of pembrolizumab (MK-3475) in subjects with relapsed or refractory classical Hodgkin lymphoma.
Treatment Assignment	Subjects meeting inclusion/exclusion criteria will be allocated to one of three cohorts, depending on their prior disease history and therapy: 
• Cohort 1: failed to achieve a response or progressed after auto-SCT and have relapsed after treatment with or failed to respond to brentuximab vedotin post auto-SCT.• Cohort 2: unable to achieve a CR or PR to salvage chemotherapy for an auto-SCT and did not receive auto-SCT, but have relapsed after treatment with or failed to respond to brentuximab vedotin.• Cohort 3: failed to respond to or progressed after auto-SCT and have not received brentuximab vedotin post auto-SCT. These subjects may or may not have received brentuximab vedotin as part of primary treatment or salvage therapy.
Analysis Populations	Efficacy: All Subjects as Treated (ASaT) Safety: All Subjects as Treated (ASaT)

Primary Endpoint(s)	The primary efficacy endpoint is the Overall Response Rate (ORR), defined as the proportion of subjects in the analysis population who have complete remission (CR) or partial remission (PR) using IWG criteria, Cheson 2007 at any time during the study. Response for the primary analysis will be determined by central review.
Key Secondary Endpoints	1. Complete Remission Rate 2. Progression-free Survival 3. Duration of Response 4. Overall Survival
Statistical Methods for Key Efficacy/ Immunogenicity/ Pharmacokinetic Analyses	The primary hypothesis will be evaluated, for each Cohort separately, by comparing ORR for MK-3475 to a fixed control rate using a binomial exact test. The point estimate of the ORR will be calculated for each Cohort as well as a 95% 2-sided exact confidence interval.
Statistical Methods for Key Safety Analyses	Within each Cohort, summary statistics (counts, percentage, mean, standard deviation, etc.) will be provided for the safety endpoints as appropriate. A pooled analysis over Cohorts may be performed as well to obtain a larger safety database.
Interim Analyses	An interim analysis will be performed by the sponsor in this study for futility alone and the results will be reviewed internally. The interim analysis would be conducted when 50% of the subjects within a cohort have been evaluated for response. Details are provided in Section 8.7.
Multiplicity	No multiplicity adjustment is planned as there is a single comparison of MK-3475 using 1 endpoint in the primary hypothesis within each Cohort. Other efficacy analyses will be considered supportive and/or explanatory.
Sample Size and Power	The planned sample size is 60 subjects for each Cohort for the primary analysis. For the three cohorts, there is at least 93% power (one-sided 2.5% alpha level) within each Cohort to demonstrate that MK-3475 is superior to a fixed control rate of 20% assuming the underlying MK-3475 ORR is at least 40%.

8.2 Responsibility for Analyses/In-House Blinding

The statistical analysis of the data obtained from this study will be the responsibility of the Clinical Biostatistics department of the sponsor.

This trial is being conducted as a non-randomized open-label study, ie, subjects, investigators, and sponsor personnel will be aware of subject treatment assignments after each subject is enrolled and treatment is assigned.

8.3 Hypotheses/Estimation

Objectives and hypotheses of the study are stated in Section 3.

Unless stated otherwise, objectives will be evaluated within each Cohort. There is one hypothesis, within each Cohort, to be formally tested in this study, ie, whether the ORR is greater than a fixed control rate using the IWG criteria based on independent central review; details on how this will be tested appear below in Section 8.6.1.1. Secondary objectives,

again within each Cohort, will not involve hypothesis testing, and will assess the efficacy of pembrolizumab on secondary efficacy endpoints (CRR, PFS, DOR, and OS) and will include, where appropriate, assessments based on investigator and Lugano classification; details appear below in the corresponding sections of Section 8.6.1.

8.4 Analysis Endpoints

Efficacy and safety endpoints that will be evaluated are listed below.

8.4.1 Efficacy Endpoints

Efficacy endpoints that will be evaluated are listed below, followed by the descriptions of the derivations of selected endpoints.

The primary efficacy endpoint is the Overall Response Rate (ORR), defined as the proportion of subjects in the analysis population who have complete remission (CR) or partial remission (PR) using IWG criteria (Cheson 2007) at any time during the study. Response for the primary analysis will be determined by central review.

Secondary efficacy endpoints include: (1) ORR according to investigator (site) assessment using IWG criteria; (2) ORR according to central review using Lugano 5-point classification; (3) complete remission rate (CRR), defined as the proportion of subjects in the analysis population who have complete remission (CR) by IWG criteria; (4) progression-free survival (PFS), defined as the time from first dose to the first documented disease progression according to IWG criteria or death due to any cause, whichever occurs first; (5) duration of response (DOR), defined as time from first IWG response to disease progression in subjects who achieve a PR or better, and (6) overall survival (OS), defined as time from first dose to date of death.

Exploratory efficacy endpoints include: (1) eligibility for SCT post-study therapy (yes/no); (2) receiving SCT following post-study therapy (yes/no); (3) ORR, (4) DOR, (5) CRR, and (6) PFS, incorporating response assessments for subjects continuing pembrolizumab treatment after initial progression.

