3.3 Exploratory Objectives

Within each of, and potentially pooled over, the 3 cohorts of subjects with R/R cHL:

(1) **Objective:** To evaluate ORR, CRR, PFS and DOR for subjects who continue treatment with pembrolizumab beyond documented progression (see Section 8.6.1).

(2) **Objective:** To explore the PK profile of pembrolizumab (see Section 7.1.3.2.1)

- (3) **Objective:** To evaluate changes in health-related quality-of-life assessments from baseline using the EORTC QLQ-C30 and EuroQol EQ-5D (see Section 4.2.3.2.1.2)
- (4) **Objective:** To further evaluate pembrolizumab immunogenicity and exposure of the proposed dose and dosing regimen (see Section 4.2.3.3).
- (5) **Objective:** To compare the extent of pre-pembrolizumab PD-L1 expression in tumor biopsies for pembrolizumab responders versus non-responders (see Section 4.2.3.2.1.1)
- (6) **Objective:** To investigate the relationship between candidate efficacy biomarkers and anti-tumor activity of pembrolizumab utilizing pre- and post-treatment lymph node biopsies and blood sampling (see Section 4.2.3.4).
- (7) **Objective:** To explore the relationship between genetic variation and response to the treatment(s) administered. Variation across the human genome will be analyzed for association with clinical data collected in this study (See Section 4.2.3.4).

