4.2.3.2 Efficacy Endpoints

The primary efficacy objective of this study is to evaluate the anti-tumor activity of pembrolizumab in subjects with relapsed or refractory classical Hodgkin lymphoma. The primary efficacy endpoint for Hodgkin lymphoma will be overall response rate (ORR) as assessed by independent central review per Cheson 2007 International Working Group (IWG) response criteria for malignant lymphoma [40]. ORR will also be assessed using the 5-point scale per the Lugano Classification [41] by independent central review as a secondary endpoint.

Immunotherapeutic agents such as pembrolizumab may produce antitumor effects by potentiating endogenous cancer-specific immune responses, which may be functionally anergic. The response patterns seen with such an approach may extend beyond the typical time course of responses seen with cytotoxic agents, and can manifest a clinical response after an initial increase in tumor burden or even the appearance of new lesions.

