8.6.1.1 Overall Response Rate (ORR)

The primary efficacy endpoint for this study is the Overall Response Rate (ORR), defined as the proportion of subjects who have response (CR or PR) according to the IWG criteria, and will be analyzed separately by cohort. The primary analysis will be conducted for that cohort when the last subject in that cohort has reached the Week 12 response assessment or has discontinued study therapy.

The analysis will consist of the point estimate and 95% 2-sided exact confidence interval (CI) using the Clopper-Pearson method which will have at least 95% coverage of the true rate. An exact binomial test will be conducted for each cohort versus a fixed control rate for each cohort.

Secondary analyses for ORR will be performed based on investigator's (ie, study site) assessment and by central review based on the Lugano Classification (JCO, 2014).

Since an investigator may still continue to treat subjects with MK-3475 who have progressed according to central review or by site assessment, exploratory analyses (point estimate and 95% 2-sided exact confidence interval) will be conducted for ORR to consider these subjects who later achieve PR or CR post-progression as responders.

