8.6.1.3 Progression-Free Survival (PFS)

The non-parametric Kaplan-Meier method will be used to estimate the PFS curve.

Since disease progression is assessed periodically, progressive disease (PD) can occur any time in the time interval between the last assessment where PD was not documented and the assessment when PD is documented. For the primary analysis, for the subjects who have PD, the true date of disease progression will be approximated by the date of the first assessment at which PD is objectively documented per IWG criteria, regardless of discontinuation of study drug. Death is always considered as a confirmed PD event.

A secondary analysis will be performed for PFS based on investigator's assessment.

In order to evaluate the robustness of the PFS endpoint, we will perform two sensitivity analyses with a different set of censoring rules. The first sensitivity analysis is the same as the primary analysis except that it censors at the last disease assessment without PD when PD or death is documented after more than one missed disease assessment. The second sensitivity analysis is the same as the primary analysis except that it considers initiation of new anticancer treatment to be a PD event for subjects without documented PD or death and lost to follow-up to be a PD event for subjects without documented PD or death and lost to follow-up after ≥ 2 missed disease assessments. The censoring rules for primary and sensitivity analyses are summarized in [Table 12](#).

Table 12 Censoring rules for Primary and Sensitivity Analyses of PFS

Situation	Primary Analysis	Sensitivity Analysis 1	Sensitivity Analysis 2
No PD and no death; new anticancer treatment is not initiated	Censored at last disease assessment	Censored at last disease assessment	Censored at last disease assessment
No PD and no death; subject receives SCT following response to pembrolizumab	Censored at last disease assessment before SCT	Censored at last disease assessment before SCT	Censored at date of SCT
No PD and no death; new anticancer treatment is initiated	Censored at last disease assessment before new anticancer treatment	Censored at last disease assessment before new anticancer treatment	Progressed at date of new anticancer treatment
PD or death documented after ≤ 1 missed disease assessment	Progressed at date of documented PD or death	Progressed at date of documented PD or death	Progressed at date of documented PD or death

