8.6.1.4 Duration of Response (DOR)

Duration of response is defined, only for the subgroup of subjects who achieve CR or PR, as the time from start of the first documentation of objective tumor response (CR or PR) to the first documentation of tumor progression or to death due to any cause, whichever comes first. The analysis will consist of Kaplan-Meier estimates. Duration of response data will be censored on the date of the last disease assessment documenting absence of progressive disease for subjects who do not have tumor progression and are still on study at the time of an analysis, are given antitumor treatment (including stem cell transplant) other than the study treatment, or are removed from study prior to documentation of tumor progression.

Duration of Response will be based upon central review according to the IWG criteria; a secondary analysis of DOR will be conducted using investigator assessment. In addition, since stem cell transplant post-initiation of MK-3475 is considered to be an indicator of positive efficacy rather than failure of the current treatment, an exploratory analysis of DOR may be conducted where date of SCT is not considered censored for those subjects; details will appear in the sSAP.

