8.7 Interim Analysis

An interim analysis will be performed within each cohort for the purpose of futility alone. The analysis will be performed and reviewed by the study team. In each cohort separately, the analysis will be performed based on response assessed by the investigators for 30 subjects. The analysis will be conducted when the 30th subject who starts study treatment for that cohort has reached the Week 12 response assessment or has discontinued study therapy prior to Week 12, ie, all 30 subjects will have been evaluated for response with at least the Week 12 response assessment or have discontinued prior to Week 12.

Enrollment into each cohort will not be paused pending the results of the analysis.

For Cohorts 1 2 and 3, if 6 or fewer responses (CR or PR at any assessment) out of 30 subjects are observed (20%), the cohort may be stopped for further enrollment. The operating characteristics of the futility stopping rule are given in [Table 14](#) below, ie, the probability of potentially stopping a cohort under the rule for a range of true ORR for MK-3475.

Table 14 Operating Characteristics of Interim Analysis Rule

True ORR	Probability of Stopping Enrollment
	Cohorts 1, 2 and 3 (if observe $\leq 6/30$ [20%])
5%	>0.99
10%	0.97
15%	0.85
20%	0.61
25%	0.35
30%	0.16
35%	0.06
40%	0.02
45%	<0.01

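### Does the primary response rate count responses first reached after progression?

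*Combined protocol and SAP*

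**What the plan says.** The primary endpoint appears in three places. Table 11 in section 8.1 takes CR or PR "using IWG criteria, Cheson 2007 at any time during the study". Section 8.4.1 says the same and adds central review: "at any time during the study. Response for the primary analysis will be determined by central review". Section 8.6.1.1 repeats the endpoint with no time window. None of the three says that a response must come before progression.

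The plan treats later responses separately. Section 3.3 has an exploratory objective: "To evaluate ORR, CRR, PFS and DOR for subjects who continue treatment with pembrolizumab beyond documented progression". Section 8.4.1 lists exploratory versions of ORR, DOR, CRR and PFS that use assessments after initial progression. Section 8.6.1.1 gives the purpose of the exploratory ORR: "to consider these subjects who later achieve PR or CR post-progression as responders".

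The time-to-event rules use first progression. For PFS, section 8.6.1.3 dates the event at "the date of the first assessment at which PD is objectively documented per IWG criteria, regardless of discontinuation of study drug". For DOR, section 8.6.1.4 runs from first response "to the first documentation of tumor progression or to death due to any cause, whichever comes first". The futility rule in section 8.7 applies "if 6 or fewer responses (CR or PR at any assessment) out of 30 subjects are observed".

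**The concern.** The wording of the primary endpoint has no upper limit, and the situation that would test it is foreseen. Section 4.2.3.2 says that responses to this kind of agent "can manifest a clinical response after an initial increase in tumor burden or even the appearance of new lesions". Note n of section 6.1 and section 7.1.2.6.7 allow a clinically stable subject to stay on drug after progression is first seen.

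Take a subject with progression at Week 12 and PR at Week 24. On the literal wording this is a primary responder. Section 8.6.1.3 already makes the subject a PFS event at Week 12. Section 8.6.1.4 cannot give a duration, because first progression precedes first response, yet Table 13 takes all responders into the DOR analysis. The CRR definition has no cut-off either.

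ORR carries the only formal test in each cohort. If two analysts could count such subjects differently, the primary estimate would not be reproducible, and a result at the boundary could turn on the choice.

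**Working it through.** **Step 1: reproduce the plan's figures.** Inputs from sections 8.8 and 8.9: n = 60 per cohort, control rate 20%, alternative 40%, one-sided alpha 0.025, exact binomial test.

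- The critical count is the smallest r with P(X ≥ r | 60, 0.20) ≤ 0.025. P(X ≥ 18) = 0.0427 and P(X ≥ 19) = 0.0221, so r = 19.
- Power is P(X ≥ 19 | 60, 0.40) = 0.928, which matches the stated 93%.
- With stopping at 6 or fewer of 30, power is 0.922, which matches the stated 92%.
- The success count of 16/60 in section 8.8 does not fit, since P(X ≥ 16 | 60, 0.20) = 0.131. That is a separate matter; 19 is used here.

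**Step 2: the effect of one subject.** The step in ORR is 1/n: 1/60 = 1.67 points, 1/69 = 1.45, 1/81 = 1.23. The cohort sizes 69, 81 and 60 are those treated, from section 4.3. One subject decides the test only at the boundary:

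| n | One below the boundary | At the boundary |
|---|---|---|
| 60 | 18: p = 0.0427 | 19: p = 0.0221 |
| 69 | 21: p = 0.0260 | 22: p = 0.0134 |
| 81 | 24: p = 0.0251 | 25: p = 0.0135 |

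**Step 3: distance from the boundary.** Section 4.3 reports ORRs of 73.9%, 64.2% and 70.0%. The counts are 0.739 × 69 ≈ 51, 0.642 × 81 ≈ 52 and 0.700 × 60 = 42. Their sum is 145, and 145/210 = 69.0%, the pooled figure in the same section. The number of responders that would have to be post-progression only before significance is lost is:

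- Cohort 1: 51 − 21 = 30 (59% of responders)
- Cohort 2: 52 − 24 = 28 (54%)
- Cohort 3: 42 − 18 = 24 (57%)

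**Step 4: compare the two readings.** If the primary ORR already counted post-progression responses, the exploratory ORR of section 8.6.1.1 would add nobody, and the section 3.3 objective would have nothing to add on ORR. If the primary ORR stops at progression, the exploratory analysis has content, the PFS date is consistent with it, and DOR is defined for every responder. Only the second reading makes the sections fit together. The any-time phrase still has a job on that reading: response is the best over follow-up and is not tied to one visit.

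**Step 5: who could be affected.** Section 7.1.2.6.6 ends routine assessments at documented progression or new treatment, so only subjects kept on drug past progression are involved. The criteria in section 12.7 also require no new sites for PR, which limits PR after progression by new lesions.

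**The case for a change.** The strongest case for a change is that the only tested endpoint should state its own rule, and one sentence would do it at no cost in data, sample size or power. It is true that the exclusion is nowhere written.

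A numerical version assumes a pre-progression ORR of exactly 20% and adds 1, 2 or 3 post-progression responders per 60. The chance of reaching 19/60 then rises from 0.022 to 0.047, 0.088 or 0.149. These figures are correct, but they are false-positive rates only if the exclusion is the rule. Under the literal rule the true ORR would be 21.7% to 25%, which is above the null. The added numbers are assumptions, since the documents give no such rate.

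Two extensions carry little weight. Second-course responses could hardly exist at the primary test. Section 8.9 has it done once, when all subjects in the cohort have reached Week 12 or stopped therapy, whereas section 7.1.5.2.2 requires a confirmed CR, at least 24 weeks of drug and a later confirmed progression. The futility count in section 8.7 uses investigator response, is not binding and supports no inference.

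One detail does remain open. Section 8.6.1.1 speaks of progression by central review or by the site. A subject with site progression, no central progression and a later central PR could be placed either way. Tying the cut-off to the assessor of the response would be reasonable. With results already reported in section 4.3, however, it would be a new choice on the tested endpoint and more than a clarification.

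**Conclusion.** This is a gap in wording that analysts fill sensibly. The primary definition does not state a cut-off at progression, but the exploratory ORR, PFS and DOR rules together lead to one, so the plan does not contradict itself. The ordinary course is for the study report to say which rule was applied.

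The consequence is small: 1.2 to 1.7 points of ORR per affected subject, and no change in any cohort's test unless more than half of its responders (54% to 59%) responded only after progression. This rests on responder counts rebuilt from the percentages in section 4.3, and on reading the exploratory ORR as adding to the primary one. The frequency of post-progression response is not in the documents. The group is probably small, given where assessments end and what PR requires. No change to the plan is needed.
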